## **6.2 IV Administration of MSCs or Placebo**

An intravenous line will be placed into an appropriate peripheral vein with 0.9% sodium chloride solution running to keep the vein open. The study solution described above will be taken up in an 18 gauge needle into a 60 mL syringe with an eccentric (offset) tip. The needle will be removed and infusion tubing will be attached to the syringe. The syringe with infusion tubing will be placed in a metered dose syringe pump positioned horizontally with the syringe rotated such that the syringe tip is at the lowest position. The product will be infused intravenously into the subject's arm at a constant rate of approximately 2 mL/min. The applicable volume for the target dose will be delivered within 2 mL. Depending on subject's weight, up to three 60 mL syringes of product may be infused. After the entire product volume is delivered, 25 mL of LRS (without cells) will be infused at 2 mL/min to deliver cells from the infusion line for more accurate dosing. Subjects in the placebo group will receive intravenous LRS. Their syringes will be labeled as above to preserve blinding and followed by 25 mL of LRS infusion as above.

If the subject has an adverse reaction during the infusion, the infusion may be interrupted or slowed according to the severity of the reaction. All appropriate treatment will be given to reduce any discomfort and ensure the subject's safety. The infusion may be restarted, if interrupted, if the subject is not considered to be at risk by the Investigator and the subject consents.

### **6.3 Product Storage and Stability**

Once the cell suspension is prepared for administration to a subject as described above, the dose of allogeneic mesenchymal bone marrow cells will be stored at +4°C until the time of administration. All cells will be administered to the subject within 8 hours of preparation. Cells that are not used within this time period will be discarded.

### **6.4 Concomitant Medications and Rehabilitation**

Concomitant medications (any prescription and/or over-the-counter preparations) and therapies (nondrug or procedures) used by a subject while participating in this clinical trial will be optimized per the AHA Guidelines and recorded at screening and until the end of the study or the end of a subject's participation in the study.

Subjects may be administered beta-blockers, ACE inhibitors, angiotensin receptor blockers or angiotensin receptor neprilysin inhibitor, mineralocorticoid receptor antagonists, isosorbide, hydralazine, statins, or other medications, as tolerated. All other prescription and over-the-counter preparations approved by the patients' physician will be permitted.

## **7. STUDY ASSESSMENTS AND SCHEDULE**

### **7.1 General Assessments**

#### **Clinical Assessments**

- Complete medical history and concomitant medications.
- Physical and cardiac examination, including vital signs (temperature, mean arterial blood pressure, weight, heart rate, respiratory rate, oxygen saturation, LVAD parameters: pump speed, power, flow,

pulsatility).

- All-cause mortality, admission for worsening HF and all-cause admissions.
- Exercise capacity: 6 minute walk distance.
- Kansas City Cardiomyopathy Questionnaire (KCCQ) (Appendix B).
- New York Heart Association (NYHA) Classification (Appendix B).

## **Clinical Laboratory Assessments**

- Hematology (CBC): hemoglobin, hematocrit, platelet count, red blood cell count, white blood cell count, automated differential and platelet count.
- Serum Chemistry: includes sodium, potassium, chloride, bicarbonate, BUN, creatinine, glucose, calcium, magnesium, phosphorous, total bilirubin, albumin and total protein, and the following liver function tests (LFTs): alkaline phosphatase, alanine aminotransferase (ALT), and aspartate aminotransferase (AST) and lactate dehydrogenase (LDH)
- Immunoglobulin A (IgA), immunoglobulin E (IgE), immunoglobulin G (IgG), immunoglobulin M (IgM),
- Troponin I, NT-pro Brain Natriuretic Peptide (NT-proBNP) and ST 2
- CK and CK-MB
- Uric Acid
- HLA
- hsCRP
- Inflammatory/immune biomarkers:  
In-vivo immune responses.

### 1.1 Quantitative Immune Response - biomarkers Array.

At all time points blood samples from all patients will be analyzed for the following 40 immune response biomarkers. Samples from normal donors will serve as reference.

Quantibody® Human Immune Response Biomarker Array 1 Kit (RayBiotech).

CD14	CD163	CD40	CRP	E-Selectin
------	-------	------	-----	------------

Fas (TNFRSF6/Apo-1)	Fas Ligand (TNFSF6)	GCSF	ICAM-1 (CD54)	IL-1 alpha (IL-1 F1)
IL-1 beta	IL-1 R4	IL-10	IL-12 p70	IL-13
IL-18	IL-2	IL-2 R alpha	IL-4	IL-6
IL-8	Lipocalin-2	MCP-1	MCP-2	MIF
MIP-1 alpha	MIP-1 beta	Osteopontin	PAI-1	Platelet Factor 4
Procalcitonin	RAGE	Resistin	Thrombomodulin	TNF alpha
TREM-1	Troponin I	uPAR	VCAM-1	VEGF-A

1.2. Antibody Isotype assay – Analyzing the effect of treatment with MSCs on the humoral response; levels of antibodies and isotype switch.

## 2. Cellular response

At all-time points leukocytes will be isolated from blood samples and will be frozen for further analysis.

Leukocytes will be analyzed for:

Immune phenotyping by flow cytometry, to determine the effect of treatment with MSCs on the cellular immune response. (Expected effect - changing the balance from pro to anti-inflammatory phenotype).

Functional assays.

Proliferation assay – evaluating the suppressive effect of MSCs on T cells.

In-vitro cytokine secretion – testing the effect of MSCs treatment on leukocytes potential to secret cytokines following general stimulation.

Cytotoxicity assay – co-culture of leukocytes with MSCs will test the cytotoxic effect of leukocytes toward MSCs on the axis of time and repeated treatments. This assay will help evaluating the effectiveness of repeated treatments with MSCs.

## B. Future assays (Biobanking)

It is to be expected that from the blood collected (listed above in 1.1-2) for all of the analyses detailed above, approximately 20ml of serum will remain unused. We plan to bank this serum for future use. Future analyses of the serum will derive from questions that are unanticipated at the initiation of the study but that usually arise once the analyses as per protocol are performed. The availability of serum to perform these

new analyses provide the potential to importantly supplement insights we can derive from this study.

## **ECG**

A 12-lead ECG will be performed. Standard interval assessments, including QT and QTc, will be calculated from a single lead (typically lead II). QTc will be calculated on the screening ECG in order to determine if the subject meets enrollment criteria. QTc must be <550 ms in order for the subject to be randomized.

## **Echocardiography**

- A full 2D, 3D and Doppler echocardiogram will be performed at baseline and day 30, 60, 90, 180, and 360. Images will be acquired with the patient positioned in the recumbent lateral position. Left ventricular volumes will be determined at end-diastole and end-systole by quantitative biplane assessment. Endocardial borders will be manually traced from apical four-chamber and two-chamber views. Left ventricular volumes will be used to calculate LVEF using the biplane modified Simpson's summation-of-disks method recommended by the American Society of Echocardiography.
- High frame-rate images of the LV in the three apical views (4-chamber, 2-chamber, and apical long axis) and the RV in the RV focused apical long axis will be acquired for speckle tracking echocardiography. Images will be analyzed offline on a dedicated workstation using TOMTEC software (TOMTEC Corporation) for calculation of segmental and global longitudinal strain and strain rate. Global longitudinal strain and strain rate will be calculated from all 18 segments of the LV and the 6 segments of the RV. Segmental strain and strain rate will be calculated for each segment separately.

## **Gated blood pool SPECT ventriculography**

Gated blood pool SPECT ventriculography will be performed at baseline and days 90 and 180. Efficacy endpoints evaluated by quantitative 3D gated blood pool SPECT ventriculography will include: LV and RV end diastolic volumes, LV and RV end systolic volumes and global LV and RV ejection fractions.

## **Zio patch monitoring**

Patients without an ICD will undergo periods of 7 day monitoring for arrhythmias using a Zio patch (iRhythm

Technologies, Inc). For the purposes of this study, life-threatening arrhythmias are defined as hemodynamically unstable sustained ventricular tachycardia or new- onset complete heart block.

## 7.2 Schedule of Assessments

### 7.2.1 Screening, Baseline and Randomization (Day -12- -11)

- Study participants must meet eligibility criteria (inclusion/exclusion criteria review).
- Sign the written informed consent.
- Complete medical history, including medications history.
- Complete physical and cardiac examination, including vital signs (temperature, mean arterial blood pressure, weight, heart rate, respiratory rate, peripheral arterial oxygen saturation, LVAD parameters: pump speed, power, flow, pulsatility), weight, and height.
- 12-lead ECG.
- Kansas City Cardiomyopathy Questionnaire (KCCQ).
- New York Heart Association (NYHA) Classification.
- 6 minute walk test
- Clinical labs: serum chemistry including BUN & creatinine, CBC with differential, LFTs, total protein, and albumin and LDH.
  - Troponin, NT-pro Brain Natriuretic Peptide (NT-proBNP)
  - Uric acid
  - Biomarkers of inflammatory/immune response
  - HIV test
  - HS-CRP
  - Zio patch recording or ICD interrogation
  - Gated blood pool SPECT ventriculography
  - Full 2D and 3D and Doppler transthoracic echocardiography with speckle-tracking.
  - Randomization into experimental or control group

## 7.2.2 Assessments and treatment

Day 0 ± 7 Days, day 30 ± 7 Days and Day 60 ± 7 Days (day of first, second and third infusion, respectively)

### Pre-infusion:

- Review and record any changes in medical history, including concomitant medications from before visit(s).
- Measure and record weight and vital signs (temperature, mean arterial blood pressure, weight, heart rate, respiratory rate, oxygen saturation, LVAD parameters: speed, power, flow, pulsatility) after subjects rest quietly in a supine or semi-recumbent position.
- Physical and cardiac examination.
- Draw and process blood samples for IgA, IgE, IgG, IgM
- Troponin, NT-pro Brain Natriuretic Peptide (NT-proBNP) and SST2.
- CK and CK-MB
- Zio patch or ICD assessment if not still on or done from baseline visit for the Zio patch patients
- Kansas City Cardiomyopathy Questionnaire (KCCQ). (30 and 60 day only)
- New York Heart Association (NYHA) Classification. (30 and 60 day only)
- 6 minute walk test (30 and 60 day only)
- Full 2D and 3D and Doppler transthoracic echocardiography with speckle-tracking (30 and 60 day only)
- Place an IV line in the upper extremity or hand with 0.9% sodium chloride running to keep the vein open
- CBC with differential
- CMP
- Uric Acid
- HLA and HS-CRP
- Biomarkers of inflammatory/immune response: A panel of inflammatory biomarkers: CD14, CD163, CD40, CRP, E-Selectin, Fas, (TNFRSF6/Apo-1), Fas Ligand (TNFSF6), GCSF, ICAM-1 (CD54), IL-1 alpha (IL-1 F1), IL-1 beta, IL-1 R4, IL-10, IL-12 p70, IL-13, IL-18, IL-2, IL-2 R alpha, IL-4, IL-6, IL-8,

Lipocalin-2, MCP-1, MCP-2, MIF, MIP-1 alpha, MIP-1 beta, Osteopontin, PAI-1, Platelet Factor 4, Procalcitonin, RAGE, Resistin, Thrombomodulin, TNF alpha, TREM-1, Troponin I, uPAR, VCAM-1, VEGF-A using a biomarker array kit and other markers as previously detailed using a biomarker array kit.

#### **During infusion:**

- IV infusion of the study product or placebo
- Monitoring for any signs of adverse reaction, record AE/s and concomitant medications
- Record vital signs and LVAD parameters every 2 hours, and as clinically indicated
- Continuous ECG monitoring during infusion of study product
- Pulse oximetry continuously during and for 2 hours post infusion

#### **Post- infusion:**

- 12-lead ECG
- Monitoring for any signs of adverse reaction, record AE/s and concomitant medications
- Record vital signs and LVAD parameters every 2 hours till discharge
- Continuous ECG monitoring for 2 hours
- Pulse oximetry continuously for 2 hours
- Subjects will be discharged from the hospital when he/she is stable in the opinion of the investigator
- Physical exam, prior to discharge if clinically stable
- Provide subject or responsible individual accompanying the subject with the phone number for contacting the study nurse and/or investigator for any questions, concerns or changes in health status.

### **7.3 Follow-up Assessments**

#### **One week post infusion (7 days ± 2 days)**

- Biomarkers of inflammatory/immune response: A panel of inflammatory biomarkers: CD14, CD163, CD40, CRP, E-Selectin, Fas, (TNFRSF6/Apo-1), Fas Ligand (TNFSF6), GCSF, ICAM-1 (CD54), IL-1

alpha (IL-1 F1), IL-1 beta, IL-1 R4, IL-10, IL-12 p70, IL-13, IL-18, IL-2, IL-2 R alpha, IL-4, IL-6, IL-8, Lipocalin-2, MCP-1, MCP-2, MIF, MIP-1 alpha, MIP-1 beta, Osteopontin, PAI-1, Platelet Factor 4, Procalcitonin, RAGE, Resistin, Thrombomodulin, TNF alpha, TREM-1, Troponin I, uPAR, VCAM-1, VEGF-A using a biomarker array kit and other markers as previously detailed using a biomarker array kit.

#### **Day 90, 180, and 360 ( $\pm 7$ ) days post initial infusion**

- Measure and record vital signs
- 12-lead ECG
- Pulse Oximetry
- Zio patch or ICD assessment
- Record all-cause mortality, admission for worsening HF and all-cause admissions, AEs and concomitant medication use
- Physical and cardiac examination
- Changes in medical history
- Clinical labs: serum chemistry including BUN & creatinine, CBC with differential, LFTs, total protein, albumin and LDH.
- HS-CRP
- Cardiac Biomarkers: NT-pro Brain Natriuretic Peptide (NT-proBNP) and ST 2
- Biomarkers of immune response: A panel of inflammatory biomarkers: CD14, CD163, CD40, CRP, E-Selectin, Fas, (TNFRSF6/Apo-1), Fas Ligand (TNFSF6), GCSF, ICAM-1 (CD54), IL-1 alpha (IL-1 F1), IL-1 beta, IL-1 R4, IL-10, IL-12 p70, IL-13, IL-18, IL-2, IL-2 R alpha, IL-4, IL-6, IL-8, Lipocalin-2, MCP-1, MCP-2, MIF, MIP-1 alpha, MIP-1 beta, Osteopontin, PAI-1, Platelet Factor 4, Procalcitonin, RAGE, Resistin, Thrombomodulin, TNF alpha, TREM-1, Troponin I, uPAR, VCAM-1, VEGF-A using a biomarker array kit using a biomarker array kit. Antibody Isotype assays, leukocyte cytokine secretory assays, and leukocyte cytotoxic effects toward MSCs. Blood sample for IgA, IgE, IgG, IgM,

- Kansas City Cardiomyopathy Questionnaire (KCCQ)
- New York Heart Association (NYHA) Classification
- 6 minute walk test
- Full 2D and 3 D and Doppler transthoracic echocardiography with speckle-tracking.
- Gated blood pool SPECT ventriculography (only 90 and 180 days)
- Uric Acid
- HLA

#### 7.4 Early Termination Visit

- Measure and record weight and vital signs
- LVAD parameters
- 12-lead ECG
- Pulse Oximetry
- Zio patch or ICD assessment
- Record the all-cause admission for worsening HF and all-cause admissions, AEs and concomitant medication use
- Physical and cardiac examination
- Changes in medical history
- Clinical labs: serum chemistry including BUN & creatinine, CBC with differential, LFTs, total protein, albumin, LDH, and uric acid
  - Biomarkers of immune response: A panel of inflammatory biomarkers: CD14, CD163, CD40, CRP, E-Selectin, Fas, (TNFRSF6/Apo-1), Fas Ligand (TNFSF6), GCSF, ICAM-1 (CD54), IL-1 alpha (IL-1 F1), IL-1 beta, IL-1 R4, IL-10, IL-12 p70, IL-13, IL-18, IL-2, IL-2 R alpha, IL-4, IL-6, IL-8, Lipocalin-2, MCP-1, MCP-2, MIF, MIP-1 alpha, MIP-1 beta, Osteopontin, PAI-1, Platelet Factor 4, Procalcitonin, RAGE, Resistin, Thrombomodulin, TNF alpha, TREM-1, Troponin I, uPAR, VCAM-1, VEGF-A using a biomarker array kit. Antibody Isotype assays, leukocyte proliferation and cytokine secretory assays, and leukocyte cytotoxic effects toward MSCs. Hs-CRP
- Blood sample for IgA, IgE, IgG

IgM 6 minute walk test

- Kansas City Cardiomyopathy Questionnaire (KCCQ)
- New York Heart Association (NYHA) Classification
- Full 2D and 3D and Doppler transthoracic echocardiography with speckle-tracking
- Cardiac Biomarkers:NT-pro Brain Natriuretic Peptide (NT-proBNP) and ST 2
- Gated blood pool SPECT ventriculography

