***Patients with Chronic Obstruction Pulmonary Disease (an immunocompetent cohort of patients).***

Sixty-two patients with chronic obstruction pulmonary disease (COPD) were randomized to double-blinded IV infusions of either allogeneic MSCs or vehicle control. Patients received four monthly infusions ( $100 \times 10^6$  cells/infusion) and were subsequently followed for 2 years. The authors report that "There were no infusional toxicities and no deaths or serious adverse events (SAEs) deemed related to MSC administration. There were no significant differences in the overall number of adverse events, frequency of COPD exacerbations, or worsening of disease in patients treated with MSCs."

In our study, during MSC infusion, we will carefully observe our patients to determine whether clinically important safety-related immune response issues arise acutely.

We will also test for long-term development of immune cell reactivity, development of anti-HLA antibodies, and whether any positive test responses are associated with adverse clinical outcomes.

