## 4.2 Endpoints

### PRIMARY ENDPOINT

#### **Safety of MSCs assessed at the following time-intervals:**

Baseline and days 30, 60, 90, 180, and 360 post-initial infusion

1. Procedural complications
2. Vital signs
  - a. Temperature
  - b. Mean arterial blood pressure
  - c. Heart rate
  - d. Respiratory rate
  - e. Weight
  - f. LVAD parameters: Pump speed, flow, pulsatility and power
3. Uncontrolled systemic infection.
4. Hemodynamically unstable clinical arrhythmias that require appropriate defibrillator shock, anti-tachycardia pacing or initiation or escalation of antiarrhythmic medications.
5. Laboratory tests
  - a. Complete blood count (CBC)/ differential.
  - b. Comprehensive Metabolic Panel: Sodium, potassium, chloride, bicarbonate, blood urea nitrogen (BUN), creatinine, glucose, calcium, magnesium and liver function tests (ALT, AST, alkaline phosphatase, bilirubin and albumin)
  - c. Troponin-I.
  - d. Allosensitization (change in antibodies against HLA (panel reactive antibody test) from baseline for strong HLA antibody specificities (MFI>2000))
6. Electrocardiogram.
7. All-cause mortality. This will be reviewed by the DSMB. The LVAD population is a high risk group with very

high mortality, which will be taken into account when reviewing safety. Survival rate among HF patients with LVAD is 95% at 1 month, 81% at 1 year, 70% at 2 years, 59% at 3 years and 49% at 4 years. For patients enrolled within our study window, we would expect a 20% mortality rate in our patient population.

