## **5.3 Subject Discontinuation and Withdrawal**

Subjects have the right to withdraw from the study at any time. Subjects will be given the option to provide a reason for withdrawal. In case of early withdrawal, the reason for withdrawal will be recorded on the appropriate Case report form (CRF). Attempts to complete early termination exam as defined in 7.4 will be made. The Investigator has the right to discontinue a subject from the study for any medical reason that the investigator determines may jeopardize the subject's safety if he or she continues in the study, or for reasons of noncompliance (e.g., missed visits, use of other investigational drugs, etc.).

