## **9 STATISTICAL CONSIDERATIONS**

Statistical analyses will be descriptive. Summary statistics will consist of sample size (N), means, standard deviations, medians, and minimum and maximum values for continuous variables, and counts and percentages for categorical variables. Tables will summarize all safety and efficacy outcome measures by actual treatment received. Summary tables will indicate the number of subjects with complete data for each measurement, event or outcome. No substitutions will be made for missing data. All analyses will be based on available data.

A detailed Statistical Analysis Plan will be written prior to data analysis. Significant deviations from the original statistical analysis plan will be detailed in the final study report.

This study intentionally is not powered and will enrolled 30 patients with 15 in each of the two randomization arms.

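### The early termination visit omits the HLA antibody test although allosensitization is a primary safety item, so some living withdrawals have no HLA result after their latest infusion

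*Combined protocol and SAP*

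**What the plan says.** Section 4.2 places this laboratory item in the primary safety endpoint: "Allosensitization (change in antibodies against HLA (panel reactive antibody test) from baseline for strong HLA antibody specificities (MFI>2000". The endpoint is assessed at "Baseline and days 30, 60, 90, 180, and 360 post-initial infusion"; early termination is not among these times. Background section 8 adds the aim: "We will also test for long-term development of immune cell reactivity, development of anti-HLA antibodies", together with whether positive tests go with adverse clinical outcomes.

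The schedule has HLA in the pre-infusion list for Days 0, 30 and 60 (section 7.2.2) and again at Days 90, 180 and 360 (section 7.3). The one-week visit list in section 7.3 does not name it.

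For a patient who withdraws, section 5.3 says: "Attempts to complete early termination exam as defined in 7.4 will be made". The laboratory line of section 7.4 reads: "Clinical labs: serum chemistry including BUN & creatinine, CBC with differential, LFTs, total protein, albumin, LDH, and uric acid". The same visit also collects hs-CRP, immunoglobulins, NT-proBNP, ST2, the biomarker array and "Antibody Isotype assays, leukocyte proliferation and cytokine secretory assays, and leukocyte cytotoxic effects toward MSCs". HLA appears nowhere in section 7.4.

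On analysis, section 9 works from available data and states: "No substitutions will be made for missing data".

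**The concern.** The trial gives allogeneic cells three times, and Background section 8 concedes that the safety of multiple injections is not yet definitively established. The sponsor chose HLA antibodies as a primary safety measure. Yet the closing visit, which already draws blood for a long list of assays, leaves out that one test. Because infusion-visit samples are taken before the infusion, each sample reflects only earlier infusions. A patient who leaves between an infusion and the next scheduled draw takes the information on that infusion with them. At stake is the completeness of item 5d, and of the planned comparison of antibody results with adverse outcomes, in living patients who withdraw or are discontinued under section 5.3.

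**Working it through.** The plan states no figure on this point to reproduce; sections 9 and 9.3 say the study is not powered. The check is a comparison of the schedule entries, followed by simple arithmetic. It assumes that the bare entry HLA in the schedule means the antibody test of item 5d.

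**1. Is the blank real?** Appendix A has 13 visit columns. The HLA row has 13 cells, marked at infusions 1, 2 and 3 and at months 3, 6 and 12. The LDH and NT-proBNP rows also have 13 cells, with the same six marks plus one under Early Term. The blank is therefore not a shifted column. Section 7.4 agrees with the table, so a site following either would not draw the test.

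**2. Does another early termination test cover it?** Total immunoglobulins, isotype assays and leukocyte cytotoxicity do not measure antibodies to HLA specificities at the item 5d threshold. The frozen one-week samples (section 4.2) are for potential biomarker analysis. The banked serum (section 7.1) is for questions not anticipated at the start. Neither is a planned HLA test.

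**3. What does each leaver have?** Nominal days, HLA taken before each infusion:

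| Patient leaves | HLA results held | Absent |
|---|---|---|
| After infusion 1, before Day 30 draw | Day 0 | Any post-exposure result |
| After infusion 2, before Day 60 draw | Days 0, 30 | Any result after infusion 2 |
| After infusion 3, before Day 90 draw | Days 0, 30, 60 | Any result after infusion 3 |
| Days 90 to 180 | Days 0, 30, 60, 90 | Closing value only; last result up to 180 − 90 = 90 days old |
| Days 180 to 360 | Days 0, 30, 60, 90, 180 | Closing value only; last result up to 360 − 180 = 180 days old |

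**4. How long are the gaps?** The first three rows cover (30 − 0) + (60 − 30) + (90 − 60) = 90 nominal days, or 90/360 = 25% of follow-up. With the ±7-day windows, the gap from infusion 3 to the Day 90 draw runs from (90 − 7) − (60 + 7) = 16 days to (90 + 7) − (60 − 7) = 44 days. Delayed infusions under section 5.2 can alter this.

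**5. What could it cost in precision?** The documents forecast no withdrawals, so this is an assumed range. Let k of 15 patients in the cell arm leave before the Day 30 draw, so that n = 15 − k have a post-exposure result. If none of the n is sensitized, the one-sided 95% upper bound on the rate is 1 − 0.05^(1/n).

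| k | n | Share without result | Upper bound |
|---|---|---|---|
| 0 | 15 | 0% | 18.1% |
| 1 | 14 | 6.7% | 19.3% |
| 2 | 13 | 13.3% | 20.6% |
| 3 | 12 | 20.0% | 22.1% |
| 4 | 11 | 26.7% | 23.8% |
| 5 | 10 | 33.3% | 25.9% |

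These bounds apply only to patients with no post-exposure result at all. Patients in the other rows of step 3 still contribute, so the table overstates the loss for a mixed group of leavers.

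**The case against.** The strongest reply is that little is lost. Section 9 uses all available data, and section 9.2 summarises laboratory change to the next infusion or follow-up visit, so every HLA result before withdrawal is kept. A patient whose infusion is stopped for a reaction stays on the visit schedule (section 4, administration of MSCs), and section 5.2 keeps the Day 90 measurement whatever number of infusions was given. Intolerance alone does not send a patient to early termination. A patient leaving after Day 180 already has two results after the last scheduled infusion. The fix cannot reach deaths: section 4.2 expects 20% mortality, or 0.20 × 15 = 3 per arm. Section 5.3 promises only attempts at the visit. All of this stands, and it narrows the point to living leavers, chiefly in the three intervals before Day 90.

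Three stronger readings are tempting, and the documents support none of them:

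- That early leavers vanish from the allosensitization result. Only those leaving before the Day 30 draw have no post-exposure value.
- That the plan accepts 4 of 15 (27%) drop-outs per arm because section 5.4 names 5 or more. That section lists reasons for which the sponsor may stop the study; it is not an expected or tolerated rate. It also names 20% missing primary safety data, which is 3 of 15 if counted per arm on this item alone.
- That the result will look safer than it is. Nothing in the documents shows that leavers are more, or less, often sensitized.

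**Conclusion.** The omission is real and appears in both section 7.4 and Appendix A. No other planned early termination assay replaces the test. As written, a compliant site loses the HLA response to the latest infusion in any living patient who leaves between that infusion and the next draw. It loses the whole post-exposure response when that infusion is the first. Later leavers lose only a closing value.

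The size is bounded by the schedule (nominally 90 of 360 days) and by the arm (6.7% per patient). The count of such patients is unknown, and so is the direction of any bias. The conclusion rests on reading the schedule's HLA entry as the item 5d test, and on the leaver attending the visit. This is a worthwhile, low-cost completion of the schedule. It does not undermine the safety analysis.

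**What to change.** - Add HLA (panel reactive antibody test) to the list in section 7.4, and mark the Early Term cell of the HLA row in Appendix A.
- In the item 5d summary, report the result as a separate early termination value with time since last infusion. Do not merge it with the scheduled days or carry it as a last post-baseline value: section 4.2 fixes the assessment days, and merging would mix follow-up times. The detailed analysis plan that section 9 says will be written can hold this rule.

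The cost is one extra assay, and at most one extra tube, at each early termination visit, plus the two schedule entries and a short reporting rule. The drawback is a value taken at a non-standard follow-up time, which is why it should be shown separately. Sample size and treatment are unchanged.
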